Title: Dementia Caregiver Career Study

NCT04603482

Date: February 1, 2023

HRP- 503SBER	TEMPLATE: SBER Protocol		
Approved:	01/2019	Prior Version:	05/2018

[USE THIS SOCIAL, BEHAVIORAL, AND EDUCATIONAL PROTOCOL TEMPLATE IF YOUR PROJECT INCLUDES SURVEY, INTERVIEWS, FOCUS GROUPS OR EDUCATIONAL RESEARCH ACTIVITIES WITH NO BIOMEDICAL/CLINICAL COMPONENTS]

INSTRUCTIONS:

- Use this template to prepare a document with the information from the following sections.
- Depending on the nature of what you are doing, some sections may not be applicable to your research. If so, please mark as N/A. You may delete contents of sections, but will not be able to delete the headings of the sections.
- When you write a protocol, keep an electronic copy. You will need to modify this copy when making changes.
- Consider using a different color font for your answers.

PROTOCOL TITLE:

Self-Management Intervention: Considering Needs & Preferences of Dementia Caregivers

(aka “Caregiver Career Study”)

PRINCIPAL INVESTIGATOR

[name]
 Nursing Science
 [contact]
[contact]

UH FACULTY ADVISOR:

If the principal investigator's primary role at UH is resident, fellow or student, identify a faculty advisor.

N/A

OTHER DEPARTMENTS INVOLVED IN THIS STUDY (IF APPLICABLE):

VERSION NUMBER:

Include the version number of this protocol if assigned by an outside entity.

DATE:

V1	12/19/19
V2	Updated 1.3.20
V3	Updated 10.7.2020, 11.23.20
V4	Updated 2.18.21, 5.14.21
V5	Updated 8.29.22
V6	Updated 2.1.23

Indicate the origin of this protocol (who conceived of and leads the development of the protocol regardless of funding):

- Investigator initiated (*Investigator(s) developed protocol, regardless of funding*)
- Industry (*Pharmaceutical, Device, etc.*) (*Industry developed protocol*)
- Federal (*NIH, DOD, etc.*)
- Cooperative Group (*SWOG, GOG, etc.*)
- Other - *Please specify:*

Funding

Objectives

Our **primary aim** is to examine the effects of a health self-management intervention (Biofeedback or Resourcefulness Training) delivered by need or preference in family carers of persons with dementia on caregiving responses (**1a**) and health outcomes (**1b**) over time. We hypothesize that family carers who receive either Biofeedback Training (BF) or Resourcefulness Training (RT) based on need or preference will have better health outcomes than carers in the attention control condition, regardless of caregiving phase.

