There are several scientific premises underlying the fundamental assumptions of the proposed study:

- 1) Having an elderly family member with any form of dementia is a devastating experience that takes its toll on other family members (i.e., spouses, adult children) who assume responsibility for their care and welfare;
- 2) The caregiving career follows a long-term trajectory that may last from 4-20 years and involves a predictable downward spiral of losses in the elder's mental and physical functioning, accompanied by changes in the level of care needed by the elder;
- 3) Changes in level of care required to meet the needs of the elder over the course of dementia are reflected in a caregiving career comprised of the roles of primary caregiver (in the home), care partner (with facility placement), caretaker (following death of the loved one);
- 4) Family carers, regardless of phase in the caregiving career, are prone to experience stress and depressive thoughts and feelings that can adversely affect their physical and mental health over time; and
- 5) Existing interventions that strengthen family carer's self-management skills, including Heart Rate Biofeedback (BF) and Resourcefulness Training (RT),[©] will reduce their stress, minimize their depressive feelings, and ultimately sustain their physical and mental health at any phase of the caregiving career.

As the population >age 65 continues to age, the number of persons with Alzheimer's and other forms of dementia is expected to escalate. More than 15 million family members provide some form of care or assistance for the over 5 million American elders who have some form of dementia. Research shows that family carers provide more than 18 billion hours of informal, unpaid care for elders with dementia, constituting an annual cost to the nation that surpasses \$221 billion. In addition, the paid costs associated with health care, long-term care, and hospice for persons with Alzheimer's and other dementias are estimated to be \$214 billion each year, making dementia one of the most costly chronic illnesses in our nation. Although Medicare or Medicaid may cover up to 70% of the expenses, family carers assume remaining costs by paying out-of-pocket, contributing to additional stress on them. Thus, the tremendous societal burden associated with Alzheimer's and other forms of dementia extends well beyond those who suffer from this devastating condition.

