Based on the foregoing review, this study will: 1) include a sample of dementia carers that include caregivers (in-home), care partners (with a facility), and caretakers (bereaved) who have recently (within six months) transitioned into a new phase of their caregiving career; 2) examine the effects of two self- management interventions delivered to carers based on their need (cut score) or preference in comparison with an attention control condition; 3) explore differences in carers at the three phases of the caregiving career on caregiver responses to their recent transition and health outcomes over time; and 4) control for the effects of number of months in carer role, dementia symptom severity, and caregiving demands. As such, this will be the first study to investigate self-management interventions across all three phases of the caregiving career of dementia carers.

Inclusion and Exclusion Criteria

Directions: Describe how individuals will be screened for eligibility. Using the tables below, describe the inclusion and exclusion criteria that will define who will be included and excluded in your final study sample.

Inclusion

1. At least 18 years old
2. Have a living family member, or a recently deceased family member diagnosed with Alzheimer's disease or another dementia
3. Identify self as a primary caregiver
4. In-home **Caregivers**: must be currently providing a minimum of 4 hours per day of supervision/direct care, and have entered that role within the past six twelve months;

Care partners whose family member moved into a nursing or assisted living

HRP-503SBER	TEMPLATE: SBER Protocol		
Approved:	01/2019	Prior Version:	05/2018

facility within the past ~~six~~ twelve months, and must report visiting their care recipient at least once per week (or have similar involvement with COVID-19 restrictions).

Caretakers (i.e. bereaved) whose family member is deceased within the past ~~six~~ twelve months, and are persons with direct oversight of the deceased person's belongings, estate, finances, etc., and/or while their family member was alive, did they consider yourself a primary caregiver (whether care recipient was at home or in a facility).

5. Be capable of performing informed consent and participating in study procedures

Exclusion

1. Does not have family member with Alzheimer's disease or another dementia

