INTERVENTION: Within two weeks of the first data collection session (including study scales and HRV data collection), carers within each of the three caregiving phases (caregivers, care partners, and caretakers) will be randomly assigned using a computer program to one of three treatment groups: 1) Self-management (SM) need, 2) Self-management (SM) preference, or 3) attention control. The SM-need group will receive a self-management intervention tailored to meet their need for resourcefulness training (RT) or biofeedback (BF) as

HRP- 503SBER	TEMPLATE: SBER Protocol		
Approved:	01/2019	Prior Version:	05/2018

determined by whichever baseline cut score is lower, the Resourcefulness Scale or the SDNN parameter for age and gender. Carers randomly assigned to the SM-preference will choose to do RT or BF according to their personal preference. However, we will use minimization methods for group assignment to ensure equivalent representation across the three treatment groups, and factors likely to affect variables of interest, including carer age, gender, and race/ethnicity, in order to insure demographic similarity.

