Prior to testing the study aims, demographic profiles for caregivers, care partners, and caretakers will be created through univariate descriptive statistics, including means, standard deviations, and range of scores, and will be used to assess continuous data; frequencies and percentages will be used to describe categorical data. We will track the health conditions and the life events of all carers and dementia symptoms, level of care, and health rating of the care recipient for those who are not bereaved. However, the primary aim (**Aim 1**) is to test the effects of health self-management interventions (RT or BF) delivered based on need (i.e., cut score) or preference (i.e., personal choice) of dementia carers who have transitioned within six months to a new phase in the caregiving career (to at-home caregiver, to care partner with a facility, or to caretaker following the death of care recipient). **Aim 1** is to compare carers who are randomly assigned to the need (SM-need, preference (SM-preference) group, or an attention control condition over 3 time points (baseline, 6 months, and 12 months) on carer responses (i.e., perceived stress, depressive cognitions, and negative emotions) (**Aim 1a**), and health outcomes (health risk, and physical and mental health) (**Aim 1b**). **Aim 2** will focus on comparing caregivers, care partners, and caretakers. For **Aims 2a and 2b**, we will determine whether differences exist among caregivers, caregivers, care partners, and caretakers in carer responses (**2a**) and health outcomes (**2b**) over time. For all analyses, we will control for the effects of three covariates: months in caregiver, care partner, or caretaker role, dementia symptom severity, and caregiving demands.

For both study aims, we will use a 3 group by 3-time point Repeated Measures Analysis of Variance (RMANOVA), as well as 3 group by 3-time point Repeated Measures Analyses of

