Covariance (RMANCOVA) to control for the three covariates on carer responses (i.e., perceived stress, depressive cognitions, and negative emotions) (**Aim 1a and Aim 2a**) and health outcomes (health risk, and physical and mental health) (**Aim 1b and 2b**). We will use both analyses in a two-step process: first, we will use RMANOVA to determine if mean differences exist among the 3 groups over 3 time points. If we find mean differences, for the second step we will run RMANCOVA to identify how the covariates impact the initial findings. This controls for any confounding effects of the covariates on the repeated measures models and will also allow us to determine how much of an impact the covariates have on carer responses and health outcomes.

The RMANOVA and RMANCOVA will allow us to not only assess mean differences across time, group differences, and the interaction of time X group in order to test the trend of the means over time across the SM- need, SM-preference, and attention control condition in **Aim 1** and caregiver vs. care partner vs. caretaker in **Aim 2**. The RMANOVA and RMANCOVA not only can be used to determine if there are mean differences across the three time periods, but can also utilize orthogonal polynomial contrasts to determine whether linear and quadratic trends of the means across time are significant.

Confidentiality of Data

1. To maintain the confidentiality of the data:

I will use a unique study identifier to code individuals' identifiable data and will store the master list separate from the study data..

Other (please explain)

Provide a plan to destroy identifiers including how and when.

Identifiers in the Screening log (Box.com) and Contact Form (REDCap and CWRU BOX) will be destroyed after data collection is complete, and before the study is closed, by deleting the files.

How are you storing your electronic data?

UH Redcap

CWRU Redcap

Secure Research Environment (SRE)

CWRU Box

OnCore

UH Secure Network Drive

CWRU Secure Network Drive

Other - List storage method and provide justification:

2. Storage location of the paper research data and documents, if applicable:

Paper research data and documents will be stored in a double-locked secure environment in the following location:

France Payne Bolton School of Nursing – Health Research Campus study office

3. Will data be shared?
 Yes
1. List the exact data elements that will be shared:
2. Describe how data will be sent:
 No
 N/A

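### Carers are assigned within caregiving phase and minimised on factors including age, gender and race/ethnicity, but neither Aim 1 model contains these factors, which may cost some power

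*Combined protocol and SAP*

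**What the plan says.** **Assignment** (Study Design/Procedures, Intervention). After baseline, "carers within each of the three caregiving phases (caregivers, care partners, and caretakers) will be randomly assigned using a computer program" to need-based self-management, preference-based self-management or attention control. The same paragraph continues: "we will use minimization methods for group assignment to ensure equivalent representation across the three treatment groups", and to balance "factors likely to affect variables of interest, including carer age, gender, and race/ethnicity". The list of factors is introduced as examples, so it may not be complete. The paragraph also leaves open whether phase is a stratum or one more minimisation factor. Under either reading it governs the assignment.

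**Analysis** (Data Analysis Plan). Aim 1 has two steps.

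- Step 1 is a three-arm by three-time repeated measures ANOVA without covariates.
- Step 2 is conditional: "If we find mean differences, for the second step we will run RMANCOVA to identify how the covariates impact the initial findings".
- The covariates are fixed at three. The plan says: "For all analyses, we will control for the effects of three covariates: months in caregiver, care partner, or caretaker role", and the other two are dementia symptom severity and caregiving demands.

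Phase is the grouping factor in the separate Aim 2 model, which has no arm term.

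**Hypothesis** (Objectives). Carers who receive either intervention "will have better health outcomes than carers in the attention control condition, regardless of caregiving phase".

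**The concern.** Balancing arms on a prognostic factor reduces the true sampling variance of the arm difference. An analysis that omits the factor does not use that reduction: the factor's variance stays in the error term, the standard error is too large, and the test rejects too rarely. The protocol itself describes the minimisation factors as likely to influence the outcomes, so on its own reasoning they belong in the model.

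What is at stake is power, mainly in step 1, since step 1 also decides whether step 2 is run. A secondary matter is interpretation: Aim 1 has no phase term, so its result is an average over the three phases.

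**Working it through.** The plan gives no significance level, power, effect size or standard deviation for Aim 1, so there is no figure of its own to reproduce. The check has two parts.

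**1. Factors against model terms**

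| Factor | Used in assignment | Step 1 | Step 2 |
|---|---|---|---|
| Caregiving phase | yes | no | no |
| Age | yes | no | no |
| Gender | yes | no | no |
| Race/ethnicity | yes | no | no |
| Months in role | not named | no | yes |
| Dementia symptom severity | not named | no | yes |
| Caregiving demands | not named | no | yes |

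The two sets do not overlap.

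**2. Size of the effect**

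Assumed throughout: two-sided 5% level, and every R² (the share of variance explained by the omitted factors).

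*(a) One contrast between two arms, exact balance.* Minimisation only approximates exact balance. With balance, the unadjusted z statistic has standard deviation √(1−R²) under no effect. Then

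- type I error = 2[1 − Φ(1.96/√(1−R²))]
- power, where the adjusted test has 80%, = Φ(1.96 + 0.84 − 1.96/√(1−R²))

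| R² | Type I error | Power (adjusted = 80%) |
|---|---|---|
| 5% | 4.4% | 78.5% |
| 10% | 3.9% | 76.9% |
| 20% | 2.8% | 72.9% |
| 30% | 1.9% | 67.7% |

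For factors that shift the level of the outcome, this bears on the arm main effect.

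*(b) Time by arm.* A factor whose effect is the same at all three visits cancels from the within-person contrasts, and the simulated type I error was then 5.0–5.2% with or without the factor. To see what happens when a factor predicts change, phase was made to shift the linear trend from T1 to T3. Settings: N = 351 (nine cells of 39, close to the planned 350), within-person correlation 0.5 (assumed), a shift of 0.275 on the orthonormal linear contrast in both active arms, 20,000 runs per setting, 4-df F test.

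| R² of the linear trend | Type I without / with phase × time | Power without / with | Power lost |
|---|---|---|---|
| 0 | 0.052 / 0.052 | 0.79 / 0.79 | 0 |
| 5% | 0.047 / 0.052 | 0.781 / 0.793 | 1.2 points |
| 10% | 0.041 / 0.051 | 0.764 / 0.792 | 2.8 points |
| 20% | 0.032 / 0.052 | 0.729 / 0.787 | 5.8 points |

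*(c) A second simulation with all four factors*, allocation balanced within phase and three binary factors, and a 0.3 SD arm effect at both follow-up visits:

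- Factors shift level only, by 0.5 SD: main effect power 0.30 unadjusted against 0.47 adjusted; time-by-arm power 0.68 against 0.68.
- Factors also shift change by 0.3 SD (level 0.3 SD): time-by-arm power 0.66 against 0.68. The share explained of the baseline-to-follow-up contrast is 0.3² × 2/3 = 0.06, against a residual of 0.5, so 0.06/0.56 = 11%.
- Factors shift change by 0.5 SD (level 0.5 SD): 0.57 against 0.68. Here 0.5² × 2/3 = 0.167, and 0.167/0.667 = 25%.

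The two simulations agree in direction and rough size. A loss above about 6 points on the time-by-arm test needs factors that explain more than a fifth of the variance in change.

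**The case against.** The strongest reply is that the test that matters is hardly touched. The main effect of arm in a three-visit repeated measures model averages in the pre-treatment baseline, so it is not the natural test of treatment. The Data Analysis Plan uses time by group for the trend across arms, and stable factor effects cancel from it. The Background expects similar stress and health effects across phases. Its one contrary pattern by phase concerns sense of control, which is not a listed outcome. All of this stands, and it is why the loss is put at a few points and possibly zero.

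A reader might also infer more than the documents support:

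- *That the result would be biased, or false positives inflated.* Neither follows. Assignment is still random, and the error is on the conservative side.
- *That a conservative step 1 would block step 2.* The condition for step 2 is a finding of mean differences among groups over the time points, which a significant time-by-arm result can reasonably meet. The plan does not say which test triggers it, so blocking is possible but not established.
- *That the primary hypothesis goes untested because no arm-by-phase term is planned.* Its reference to phase can fairly mean an effect pooled over phases. The Background states benefit in any phase ("ultimately sustain their physical and mental health at any phase of the caregiving career") as a premise, and lists the aim to "explore differences in carers at the three phases of the caregiving career" separately from the intervention effects. No contradiction is shown.

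**Conclusion.** The mismatch between assignment and analysis is real and plain on the text. Its consequence is a possible loss of power, not an invalid comparison. For the time-by-arm test the simulated loss is about 1, 3 and 6 points at assumed R² of 5, 10 and 20% of the linear trend, and zero if the factors explain nothing or act equally at every visit. The arm main effect can lose more if the factors shift outcome levels. These figures rest on assumed R² values, near-equal cells, no dropout and a within-person correlation of 0.5; the documents supply none of them. The change is worth making because it costs almost nothing, not because the present plan would mislead.

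On phase, the supportable statement is narrow: Aim 1 as modelled yields an effect averaged over phases and cannot by itself support a claim that carers in each phase benefit.

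**What to change.** 1. State the complete list of factors used in the assignment, and whether phase is a stratum or a minimisation factor.
2. Include every one of them in both the step 1 and step 2 Aim 1 models: phase as at randomisation (it can change during follow-up), age, gender, race/ethnicity and any other factor on the final list, each with its interaction with time.
3. Optional and secondary: say that the Aim 1 result is pooled over phases and will not be used to claim benefit in each phase. If arm effects by phase are reported, give them with 95% confidence intervals and label them descriptive.

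**Cost.** No new data: the factors must be known before a carer can be assigned. The main terms use 2 df for phase, 1 for age if linear, 1 for gender if two categories, and one per race/ethnicity category after the first; the time interactions use twice as many. With three race/ethnicity categories (assumed) that is 2 + 1 + 1 + 2 = 6 of the 350 − 3 = 347 between-person error df, and 12 of the 2 × 347 = 694 within-person error df.

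Some scales are not given to caretakers, which may affect the existing step 2 covariates. That is a separate point, and this change does not resolve it.

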After eligibility is verified during phone screening by team member, the consent will be reviewed verbally, questions about the study will be answered. They will be asked if they verbally consent to the study, with the understanding that the Consent Form will be reviewed and signed prior to the first timepoint (T1) data collection. If they agree to participate, the research team member will then confirm and update any contact information into CWRU Box Screening and Enrollment Log and REDCap form; this includes the individual's full name, mailing address, phone number(s), email address, best time of day to call, and confirming if the study team can leave voice mail messages, text to schedule / confirm study visits and intervention check-ins, and/or send mail to their mailing address if we are having trouble contacting them by phone or email. The study enrollment/first data collection appointment will be made at this time.

If the screenee is not eligible/ declines verbal consent:

If the individual does not meet the study criteria, they are asked if they would like to have their contact information kept on file in the event that the screening criteria are modified (e.g. study radius) and would like to be contacted to re-assess eligibility. If they say yes, the staff member will proceed to collect contact information in CWRU BOX and REDCap form (confirm full name, mailing address, phone number(s), email address).

Screening data (questions asked to determine eligibility) is kept in the REDCap form in which it was entered in for tracking and reporting purposes.

5. Describe the feasibility of recruiting the required number of suitable research participants within the agreed recruitment period. For example, how many potential research participants do you have access to?

Based on previous research by the PI, we conservatively estimate that 20%–45% 58% of caregivers may not meet eligibility criteria. Thus, we will screen ~375–550 600 individuals potential participants to obtain the desired sample size of 300 350.

Setting

Directions: Make sure to describe: 1) sites and locations where your research team will conduct the research; 2) where your research team will identify and recruit potential research participants; and 3) include the physical location where research procedures will be performed.

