Carers in the SM-need and SM-preference groups will receive the training and practice a self-management intervention between the T1 and T2 data collections and may continue to use the intervention between T2 and T3 if they wish. The attention control (AC) condition, which consists of diversional activities, will also take place between T1 and T2 data collections. The RT, BF, or AC will be introduced during a single virtual session (Zoom, or iPad + phone call, depending on study participants ability / preference) during the COVID-19 pandemic, otherwise during a single face-to-face session in a mutually agreed upon private location. These intervention meetings last about 30-60 minutes and include a voice-over PowerPoint presentation, a summary of the information in a print brochure or electronic PDF, and a workbook (print or electronic) to be completed daily over 28 days, as they independently practice the intervention. RT participants will also be given a printed or emailed PDF list of examples (differ depending on caregiving type) from the training. The electronic workbook will be a form that is emailed daily over 28 days, but a print booklet will be provided for those that prefer it, and will be collected after 28 days. They will receive telephone, text or email follow-up (their preference) once per week for the 28-day intervention period while practicing the intervention (or activities) independently and keeping a daily workbook. Interventionists will be carefully trained by PI [name] and CNS [name] during a 2-day session that will include intervention delivery, cultural diversity training, and methods for providing psychological support/referral (e.g., “first call for help”) in case carers experience psychological or physical distress during the training session or 28-day intervention period. Interventionists will be blinded to fidelity measures and different interventionists will provide the RT, BF, or AC; they will keep field notes and have weekly supervision by CNS [name] and PI [name], who has been trained in delivering biofeedback and has pilot-tested both interventions for feasibility and efficacy in similar populations. Commonalities during the single session for the RT, BF, or AC are:

- 1) All carers will keep a progress log, though its content will differ by intervention/condition;
- 2) All will be taught to indicate day and time of the log entry, with the suggestion to do it at the same time each day; and

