- 3) All will complete a log entry during the training session.

Consistently, during the 4 weeks after the initial session:

- 1) All carers will perform the assigned intervention (or activities) on their own,
- 2) All will have access to intervention/activity content for review as they wish,
- 3) All will receive weekly follow-up calls/emails from interventionists (3-5 minutes) to remind them to follow respective intervention/activity protocols, and
- 4) All will be encouraged to continue their logs even if days have been missed (although BF data may be missing).

Resourcefulness Training Intervention

Resourcefulness training involves teaching skills constituting personal (self-help) and social (help-seeking) resourcefulness. The proposed method for teaching resourcefulness extends beyond simply teaching the skills to the caregivers of persons with dementia to facilitating the use of resourcefulness skills through self-reinforcement by daily tracking in a tracking log. Therefore, in this unique intervention, a mnemonic device will be used to facilitate recall of specific skills within the repertoire comprising resourcefulness. **Three** mnemonic techniques are used in (RT): acronyms, chunking, and practice. The techniques are explained on the slides.

An **acronym** is formed by the first letter of words or groups of words to form a new word. In the case of RT, the mnemonic device uses the 8 letters spelling **RESOURCE** to prompt recall of specific personal and social resourcefulness strategies as follows:

- Rely on family / friends;
- Exchange ideas with others;
- Seek professionals or experts;
- Organize daily activities;
- Use positive self-talk;
- Reframe the situation positively;
- Change from usual reaction;
- Explore new ideas.

The second mnemonic technique to be used in RT is **chunking**, which refers to the common rule that an individual can remember between 5 and 9 things at one time. In RT, the word RESOURCE contains 8 letters, which is a reasonable “chunk” of ideas of ideas for study participants to remember. Another way in which chunking is used is that the first three resourcefulness skills refer to social resourcefulness and involve help-seeking behavior, while the last five refer to personal resourcefulness and use self-help behaviors.

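### Self-management versus attention control is confounded with who delivers the sessions, and the planned model has no interventionist term, so its error bars are too narrow if interventionists differ at all

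*Combined protocol and SAP*

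**What the plan says.** Carers are randomised within caregiving phase to "1) Self-management (SM) need, 2) Self-management (SM) preference, or 3) attention control" (Study Design/Procedures, INTERVENTION). Both SM arms receive either resourcefulness training (RT) or biofeedback (BF). In SM-need the choice follows a baseline cut score; in the other arm, "Carers randomly assigned to the SM-preference will choose to do RT or BF according to their personal preference".

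On delivery, the same section states that "different interventionists will provide the RT, BF, or AC". Each carer has one session of 30 to 60 minutes built around a narrated slide presentation, and then: "All will receive weekly follow-up calls/emails from interventionists (3-5 minutes" per contact).

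The hypothesis under Objectives is that carers given RT or BF "will have better health outcomes than carers in the attention control condition, regardless of caregiving phase".

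The Data Analysis Plan states: "For both study aims, we will use a 3 group by 3-time point Repeated Measures Analysis of Variance (RMANOVA"), followed by the covariance version. On adjustment, "we will control for the effects of three covariates: months in caregiver, care partner, or caretaker role, dementia symptom severity, and caregiving demands". Interventionist is not in that list, and the section mentions no random effect, ICC or clustering allowance. Objectives says that fidelity will be measured, but the analysis section makes no use of it. The intervention-tracking items under Additional Information cover the session date and the weekly contact, not who delivered them.

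**The concern.** Carers who share an interventionist may share something of that person's effect: how clearly the session is run, how warm the weekly contact is, how strongly practice is encouraged. Where the same people serve both arms of a comparison, this largely cancels. Here it cannot cancel for either SM arm against control, because control carers see only AC interventionists and SM carers see only RT or BF interventionists.

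Two things follow for the main Aim 1 contrast. An unusually good or poor control interventionist could hide or create a benefit. And a standard error that assumes independent carers omits the between-interventionist variance. That omitted part shrinks with more interventionists, not with more carers, so about 117 carers per arm spread over a few people makes even a small ICC matter.

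**Working it through.** **Inputs from the documents.** The recruitment feasibility text screens people "to obtain the desired sample size of 300 350", where 300 is the superseded figure and 350 is current. The three arms, the separate delivery and the analysis model are as quoted above.

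**Assumptions.** Equal allocation, so 350/3 = 116.7, taken as n = 117 per arm. RT:BF split 50:50 within an SM arm. k interventionists for each of RT, BF and AC, with equal caseloads. Total variance 1, two-sided 5% test, ICC from 0 to 0.02. The documents give no alpha, power, SD, ICC or k, so there is no figure of the plan's own to reproduce.

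**One SM arm versus attention control, one post-treatment score.**

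- Variance assumed by an independent-carer analysis: 2/n = 2/117 = 0.01709.
- True variance: (1 − ICC) × 2/n + ICC/k + 0.5 × ICC/k. The last two terms are the AC interventionists, and the RT and BF interventionists at half weight each (0.25 + 0.25 = 0.5).
- True error: 2 × [1 − Φ(1.96 × √(assumed/true))].

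Example, k = 2 and ICC 0.01: 0.99 × 0.01709 + 1.5 × 0.01/2 = 0.01692 + 0.00750 = 0.02442. The ratio is 0.02442/0.01709 = 1.43, the SE factor √1.43 = 1.195, and 1.96/1.195 = 1.64, so the error is 10%.

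| ICC | k = 1 | k = 2 | k = 5 |
|---|---|---|---|
| 0 | 5% | 5% | 5% |
| 0.01 | 15% (variance ×1.87) | 10% (×1.43) | 7% (×1.17) |
| 0.02 | 24% (×2.73) | 15% (×1.86) | 9% (×1.33) |

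**Omnibus three-group test.** Simulated on one post-treatment score, 20,000 runs per case. At ICC 0.01 the error is 15%, 10% and 8% for k = 1, 2 and 3; at ICC 0.02 it is 24%, 15% and 12%.

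**SM-need versus SM-preference.** With the same RT:BF mix the shared interventionist effects cancel, leaving (1 − ICC) × 2/n, slightly below the assumed variance. Simulated error is 4.8% to 5.1% at ICC 0.01 to 0.02. If the mixes differ, for example 70:30 against 40:60, the extra term is 2 × 0.3² × ICC/k. At ICC 0.02 the error is then 7% (k = 1) or 6% (k = 2).

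**Aim 2.** Randomisation is within caregiving phase, so each phase contains all three arms and interventionists are not nested in phase by design.

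**Cost of modelling it.** A difference of (1.96 + 0.84) × √(2/116.7) = 0.367 SD has 80% power if carers are independent. With a random interventionist effect and 3(k − 1) degrees of freedom, power is about 48% at k = 2 (3 df) even if the true ICC is 0, and 30% at ICC 0.02. At k = 3 (6 df) it is 65% and 47%. The ANOVA estimate of the interventionist variance is zero or negative in about 40% of trials at k = 2, ICC 0.01, and about 23% at k = 5, ICC 0.02.

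**The case against.** The strongest reply is that the ICC may be negligible. Interventionists have two days of training and weekly supervision, the session uses narrated slides with printed or electronic materials, weekly contact is short and may be by text or email, and carers practise on their own. Outcomes are taken months later, so an interventionist effect would have to last. This stands as a reason to expect the low end of the table; it does not show that the ICC is zero.

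Second, the calculation is not the planned test. The 3 × 3 model includes a baseline taken before any interventionist contact and tests group, time and their interaction; the relevant ICC is that of change or of averaged scores. This stands: the planned test may be affected more or less than shown.

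Third, if these particular interventionists are regarded as part of the treatment, the independent-carer standard error is adequate for that narrower claim. This also stands, but the confounding remains and the conclusion would have to be worded to match.

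Fourth, a random-effect model as the primary analysis would cost much power, as shown above. This is a good reason not to replace the primary model. Separate delivery is itself a reasonable guard against contamination and need not change.

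**Conclusion.** The point holds for SM-need versus attention control, SM-preference versus attention control and the omnibus group test. As planned, these cannot be separated from interventionist differences, and their error bars are too narrow if interventionists differ at all. Under the stated assumptions, a nominal 5% test has true error of about 7% to 24% for ICC 0.01 to 0.02 and one to five interventionists per condition, and exactly 5% at ICC 0.

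A reader might infer that every comparison in the trial has understated error, or that the error is known to be inflated. The documents do not support either. The randomised arms are not RT, BF and AC; the two SM arms draw on the same RT and BF interventionists; and Aim 2 compares phases that are not nested in interventionist. No ICC or interventionist count is given, so the inflation is conditional and its size is an illustration.

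**What to change.** 1. Add an interventionist ID to the intervention-tracking form for every carer, and state the number of interventionists per condition. Interventionists' field notes might allow this to be rebuilt later, but the ID is not among the listed tracking items.
2. Keep the planned RMANOVA/RMANCOVA. Pre-specify a sensitivity analysis of each SM arm versus attention control with a random interventionist effect nested in RT, BF or AC and small-sample degrees of freedom.
3. Because the ICC will be poorly estimated with few interventionists, also report the same contrasts over a range of assumed ICCs, for example 0 to 0.05.
4. If a condition has only one interventionist, or the result does not survive plausible ICCs, say in the conclusion that the arm effect includes the interventionist.

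This is a cheap improvement: one form field and a paragraph of analysis text, with no change to delivery or sample size. The downside is wider intervals and low power in the sensitivity analysis when interventionists are few.
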